9.7.2 Determination of Sample Size

A sample size of 60 subjects is sufficient to detect a 100% complete clearance rate at Day 57 greater than 20% with 80% power, based on a two-sided ($\alpha=0.05$) binomial test, assuming a response rate of 35%, and less than a 25% dropout rate. This corresponds to a two-sided 95% CI with a half-width of less than 15% (ie, lower boundary of the CI above 20%).

9.7.3 Interim Analysis

Since this is an open-label study, after each group of 20 subjects completes Day 57 assessments, activity data will be tabulated.

9.7.4 Other Statistical/Analytical Issues

Not applicable

9.7.5 Procedure for Revising the Statistical Analysis Plan

If the prespecified plans need to be revised after the study starts, the Sponsor will determine how the revision impacts the study and how the revision should be implemented. The details of the revision will be documented and described in the clinical study report.

11 APPENDICES

Appendix 1 Fitzpatrick Skin-Type Classification

Australian Government
Australian Radiation Protection
and Nuclear Safety Agency

Fitzpatrick Skin Type

The most commonly used scheme to classify a person's skin type by their response to sun exposure in terms of the degree of burning and tanning was developed by Thomas B. Fitzpatrick*, MD, PhD. Examples are given below.

[figure not shown]

[figure not shown]
[figure not shown]

[figure not shown]
[figure not shown]
[figure not shown]

[figure not shown]

[figure not shown]
[figure not shown]

[figure not shown]

[figure not shown]
[figure not shown]
[figure not shown]
* Fitzpatrick, T.B. (1988) The validity and practicality of sun reactive skin types I through VI. Arch Dermatol 124; 869-871.


Eye colour
 
0. Light colours 1. Blue, gray or green 2. Dark 3. Brown 4. Black
	
Do you turn brown?
 
0. Never 1. Seldom 2. Sometimes 3. Often 4. Always
	
Score
 
 
 0-6	Skin Type I		
 
 Always burns, never tans (pale white skin)	
 
 7-13	Skin Type II		
 
 Always burns easily, tans minimally (white skin)	
 
 14-20	Skin Type III		
 
 Burns moderately, tans uniformly (light brown skin)	
 
 21-27	Skin Type IV		
 
 Burns minimally, always tans well (moderate brown skin)	
 
 28-34	Skin Type V		
 
 Rarely burns, tans profusely (dark brown skin)	
 
 35+	Skin Type VI		
 
 Never burns (deeply pigmented dark brown to black skin)	
 
	0-6	Skin Type I		Always burns, never tans (pale white skin)		7-13	Skin Type II		Always burns easily, tans minimally (white skin)		14-20	Skin Type III		Burns moderately, tans uniformly (light brown skin)		21-27	Skin Type IV		Burns minimally, always tans well (moderate brown skin)		28-34	Skin Type V		Rarely burns, tans profusely (dark brown skin)		35+	Skin Type VI		Never burns (deeply pigmented dark brown to black skin)		
0-6	Skin Type I																																
Always burns, never tans (pale white skin)																																	
7-13	Skin Type II																																
Always burns easily, tans minimally (white skin)																																	
14-20	Skin Type III																																
Burns moderately, tans uniformly (light brown skin)																																	
21-27	Skin Type IV																																
Burns minimally, always tans well (moderate brown skin)																																	
28-34	Skin Type V																																
Rarely burns, tans profusely (dark brown skin)																																	
35+	Skin Type VI																																
Never burns (deeply pigmented dark brown to black skin)																																	

Natural hair colour
 
0. Sandy red 1. Blond 2. Chestnut or dark blond 3. Brown 4. Black
	
How brown do you get?
 
0. Never 1. Light tan 2. Medium tan 3. Dark tan 4. Deep dark
																																

Your skin colour (unexposed areas)
 
0. Reddish 1. Pale 2. Beige or olive 3. Brown 4. Dark brown
	
Is your face sensitive to the sun?
 
0. Very sensitive 1. Sensitive 2. Sometimes 3. Resistant 4. Never have a problem
																																

Freckles (unexposed areas)
 
0. Many 1. Several 2. Few 3. Rare 4. None
	
How often do you tan?
 
0. Never 1. Seldom 2. Sometimes 3. Often 4. Always
																																

If you stay in the sun too long?
 
0. Painful blisters, peeling 1. Mild blisters, peeling 2. Burn, mild peeling 3. Rare 4. No burning
	
When was your last tan?
 
0. +3 months ago 1. 2-3 months ago 2. 1-2 months ago 3. Weeks ago 4. Days
																																

Images sourced from iStockphoto

* The information published here is not intended to take the place of medical advice. Please seek advice from a qualified health care professional.

Appendix 2 Photographs of Local Skin Reactions

Grade	0	1	2	3	4
Erythema	 Not present	 Slightly pink <50%	 Pink or light red >50%	 Red, restricted to treatment area	 Red extending outside treatment area
Flaking/Scaling	 Not present	 Isolated scale, specific to lesions	 Scale <50%	 Scale >50%	 Scaling extending outside treatment area
Crusting	 Not present	 Isolated crusting	 Crusting <50%	 Crusting >50%	 Crusting extending outside treatment area
Swelling	 Not present	 Slight, lesion specific oedema	 Palpable oedema extending beyond individual lesions	 Confluent and/or visible oedema	 Marked swelling extending outside treatment area
Vesiculation/ Pustulation	 Not present	 Vesicles only	 Transudate or pustules, with or without vesicles <50%	 Transudate or pustules, with or without vesicles >50%	 Transudate or pustules, with or without vesicles extending outside treatment area
Erosion/ Ulceration	 Not present	 Lesion specific erosion	 Erosion extending beyond individual lesions	 Erosion >50%	 Black eschar or ulceration

Source: (CDER) Clinical Review NDA 202833 PICATO™ (ingenol mebutate gel, PEP005 Gel) November 30, 2011.

2 LIST OF ABBREVIATIONS AND DEFINITIONS OF TERMS

Abbreviation	Term
AE	adverse event
AK	actinic keratosis
ADS	analysis data specifications
CI	confidence interval
LSR	local skin reaction
LOCF	last observation carried forward
PT	preferred term
SAP	statistical analysis plan
SD	standard deviation
SOC	system organ class
TEAE	treatment-emergent adverse event

3 INTRODUCTION

This Statistical Analysis Plan (SAP) is based on the protocol for study KX01-AK-002 Amendment 2, v3.0, dated 26SEP2016. This SAP supersedes the statistical section of the protocol and provides data analysis details for the activity and safety data analysis in the clinical study report (CSR). It does not include information regarding the pharmacokinetic (PK) analysis of the study drug, KX2-391 Ointment 1.0%; that information is provided separately.

3.1 Study Objectives

As stated above, objectives related to the PK analysis are not discussed in this document.

3.1.1 Primary Objective

- To evaluate the activity of KX2-391 Ointment 1% administered topically to the face or scalp in subjects with actinic keratosis (AK) by determining complete response rate, defined as 100% clearance at Day 57

3.1.2 Secondary Objectives

- To assess the activity of KX2-391 Ointment 1% during Days 1-57
- To assess the safety and tolerability of KX2-391 Ointment 1% in subjects with AK on the face or scalp
- To assess dose regimens by contrasting 5-day treatment with 3-day treatment in terms of the activity and safety of KX2-391 Ointment 1% in subjects with AK on the face or scalp

3.1.3 Exploratory Objectives

- To determine recurrence rates up to 12 months post-Day 57 for subjects who show response at Day 57
- To determine sustained response rates at 12 months post-Day 57 for subjects who show response at Day 57

3.2 Overall Study Design and Plan

This is an open-label, multicenter, activity, safety, tolerability, and PK study of KX2-391 Ointment 1% administered topically to the face or scalp of subjects with actinic keratosis in 2 sequential cohorts: a 5-day dosing regimen (Cohort 1) and a 3-day dosing regimen (Cohort 2).

The study consists of Screening, Treatment, Follow-up, and Recurrence Follow-up Periods.

In Cohort 1, eligible subjects will receive 5 consecutive days of topical treatment, to be applied at the study site, with 50 mg of KX2-391 Ointment 1% each day. Blood samples for PK analysis will be collected on Day 1 and Day 5. Subjects will return for Follow-up visits until

Day 57. Only Day 57 complete responders will continue Recurrence Follow-up Visits every 3 months for an additional 12 months after Day 57. Activity (lesion counts) and safety evaluations will be performed.

The Sponsor will review accumulating data. If the 5-day regimen (Cohort 1) has sufficient activity and safety to warrant evaluating a 3-day regimen, enrollment of Cohort 2 will start after there are 60 evaluable subjects or up to 80 subjects are enrolled (whichever comes first) in Cohort 1. For the most part, protocol procedures for Cohort 1 will be duplicated for Cohort 2, except PK samples will be collected on Days 1 and 3, and subjects will not return for Visits 5 and 6.

4 DETERMINATION OF SAMPLE SIZE

For either cohort, a sample size of 60 subjects is sufficient to detect a 100% clearance rate at Day 57 greater than 20% with 80% power, based on a two-sided ($\alpha=0.05$) binomial test, assuming a response rate of 35%, and less than a 25% dropout rate. This corresponds to a two-sided 95% confidence interval (CI) with a half-width of less than 15% (ie, lower boundary of the CI above 20%). The sample size of Cohort 2 may be adjusted, depending on the results of Cohort 1.

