In each cohort, approximately 80 subjects will be enrolled to provide approximately 60 subjects in the Evaluable Set, defined as subjects who complete all planned treatments and most evaluations, including the Day 57 Follow-up visit. Therefore, a total of 160 subjects in 2 cohorts may be enrolled, but the sample size of Cohort 2 may be adjusted, depending on the results of Cohort 1.

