9.7.2 Determination of Sample Size

For either cohort, a sample size of 60 subjects is sufficient to detect a 100% complete clearance rate at Day 57 greater than 20% with 80% power, based on a two-sided ($\alpha=0.05$) binomial test, assuming a response rate of 35%, and less than a 25% dropout rate. This corresponds to a two-sided 95% CI with a half-width of less than 15% (ie, lower boundary of the CI above 20%).

The sample size of Cohort 2 may be adjusted, depending on the results of Cohort 1.

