5.4 Activity Analyses

5.4.1 Primary Activity Analyses

The proportion of subjects with 100% clearance of all treated AK lesions at Day 57 will be considered to follow a binomial distribution. Based on the number of subjects who achieved 100% clearance at Day 57, the complete response rate and its corresponding 95% Clopper-Pearson Exact CI will be estimated in the Evaluable Set.

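### The stated 80% power is about 75%: with 60 evaluable subjects, 19 responders are needed to exclude 20%, and a true 35% rate gives that 74.8% of the time

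*SAP*

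**What the plan says.** SAP section 4 says that "a sample size of 60 subjects is sufficient to detect a 100% clearance rate at Day 57 greater than 20% with 80% power". The test is a two-sided binomial test at alpha 0.05, "assuming a response rate of 35%, and less than a 25% dropout rate". Protocol 9.7.2, and the sample size rationale in the protocol synopsis, make the same statement: "a sample size of 60 subjects is sufficient to detect a 100% complete clearance rate at Day 57 greater than 20% with 80% power".

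SAP section 4 then links the power to an interval: "This corresponds to a two-sided 95% confidence interval (CI) with a half-width of less than 15% (ie, lower boundary of the CI above 20" (the last figure is a percentage).

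The 60 are subjects left after dropout. Protocol 9.1 says that in each cohort "approximately 80 subjects will be enrolled to provide approximately 60 subjects in the Evaluable Set", and 80 × 0.75 = 60. SAP 5.4.1 fixes the primary analysis: "the complete response rate and its corresponding 95% Clopper-Pearson Exact CI will be estimated in the Evaluable Set".

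**The concern.** Every input to the power figure is given, so it can be recomputed, and the exact calculation does not return 80%. The statement applies to each cohort. It also equates the power with the lower confidence limit lying above 20%, so it tells the reader how likely each cohort is to meet that mark. If the true power is lower, the risk of missing the mark at the assumed 35% rate is understated. SAP section 4 also allows Cohort 2 to be resized after Cohort 1, and anyone resizing it from this paragraph would start from an overstated figure. The sentence on half-width could be taken as support for the 80%, so it needs checking too.

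**Working it through.** **Inputs** (SAP section 4 unless noted): n = 60 evaluable; null rate 20%; assumed true rate 35%; two-sided alpha 0.05; stated power 80%; success on the interval scale means a lower 95% limit above 20%; the interval is Clopper-Pearson (SAP 5.4.1).

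**1. Trying to reproduce 80%.** The closest standard route is the uncorrected normal formula for one proportion, with the null variance under the null:

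Power = Φ{[(0.35 − 0.20) − 1.96·√(0.20·0.80/60)] / √(0.35·0.65/60)} = Φ{(0.15 − 0.1012)/0.0616} = Φ(0.792) = 78.6%.

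This formula first reaches 80% at n = 63. Other variants at n = 60:
- with continuity correction: 74.4%
- arcsine: 74.7%
- one-sided 5% exact test (cut-off 18): 82.8%, but the text says two-sided

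**2. The cut-off at n = 60.** Each criterion was checked at 18 and 19 responders:

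| Criterion | 18/60 | 19/60 | Needed |
|---|---|---|---|
| Upper tail, P(X ≥ x given 20%) | 0.0427 | 0.0221 | ≤ 0.025 |
| Two-sided exact p (sum of outcomes no more likely) | 0.074 | 0.034 | ≤ 0.05 |
| Clopper-Pearson lower limit | 18.85% | 20.26% | > 20% |
| Uncorrected z, (x/60 − 0.20)/√(0.16/60) | 1.94 | 2.26 | ≥ 1.96 |

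All four give the same cut-off of 19 (19/60 = 31.7%), so the version of the test does not matter at this sample size.

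**3. Power.** P(X ≥ 19 given n = 60, rate 35%) = 74.8%. Adding the lower rejection region (5 or fewer responders) changes this by less than 0.001 percentage points. The shortfall is 80 − 74.8 = 5.2 points. The z-test also needs 19, so its actual rejection probability is 74.8% too, although its formula returns 78.6%.

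**4. The half-width statement.** The Clopper-Pearson half-width at n = 60 is at most 13.2 points (at 30/60), so the claim of less than 15 is true. At 21/60 = 35% the interval is 23.1% to 48.4%. At 18/60 it is 18.85% to 43.21%. That half-width is (43.21 − 18.85)/2 = 12.2 points, yet the lower limit is below 20%. A half-width under 15 points therefore does not ensure a lower limit above 20%; 19 responders do.

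**5. Dependence on the number reached.** The plan is for approximately 60. For the equal-tailed exact test, which has the same cut-off as the Clopper-Pearson criterion at every n from 56 to 81, power at 35% is:

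| Evaluable n | 59 | 60 | 61 | 64 | 68 | 72 | 77 | 80 |
|---|---|---|---|---|---|---|---|---|
| Power | 71.8% | 74.8% | 68.6% | 77.5% | 79.8% | 81.9% | 79.4% | 85.5% |

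Between 60 and 80 it is at least 80% only at 72, 75, 76, 78, 79 and 80.

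**The case against.** The documents say binomial test, not exact binomial test, and the protocol names no interval method; Clopper-Pearson appears only in the SAP. On that reading, 80% is a rounded result of a common planning formula (78.6%) and the fault is an unlabelled approximation. This explains where the figure probably came from but does not rescue it. No section names an approximation, 78.6% is still below 80%, and the approximate test at n = 60 has the same cut-off and the same true power of 74.8%.

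The sample size is only approximate, and for the uncorrected z-test n = 60 is a local low: its true power is 80.4% at 59, 77.6% at 61 and 80.2% at 62. That is correct, but the true two-sided error rate of that test at those sizes is 5.05%, 5.33% and 5.46%, slightly above the stated 5%, and it is not the planned interval criterion. What stands is that figures for other sample sizes must say which test they describe. At 61, for example, an exact two-sided p-value that sums the less likely outcomes has a cut-off of 19 and power of 77.6%, against 68.6% for the Clopper-Pearson criterion.

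The half-width sentence is true at an observed 35%. That stands too, and the sentence can stay as a statement of precision.

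Finally, little depends on the figure. The analysis sections plan no test against 20%, cohort contrasts are mainly descriptive, and Cohort 2 opens on the sponsor's review of activity and safety. SAP 5.2.6.1 also reports doses already given in both cohorts, so the restatement cannot change the design. All of this limits the impact. It does not make the figure right.

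**Conclusion.** The concern holds. For the test, sample size and interval that the documents specify, power is 74.8%, not 80%, at exactly 60 evaluable subjects and a true rate of 35%. At that rate, the chance that a cohort's lower limit does not exceed 20% is about 25% rather than 20%. No outside figure is needed: every input is in SAP section 4 and SAP 5.4.1. The result is conditional on reaching 60, and by the Clopper-Pearson criterion power would be 68.6% at 61 or 85.5% at 80. The error should be corrected, but its reach is small: no estimate, interval or analysis changes.

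**What to change.** Restate the power in SAP section 4, Protocol 9.7.2 and the synopsis, for example:

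> Sixty evaluable subjects give about 75% power (exact binomial, two-sided 5%) for a true rate of 35% against 20%. At least 19/60 responders (31.7%) are needed for the Clopper-Pearson 95% lower limit to exceed 20%; an observed 21/60 gives an interval of 23.1% to 48.4%. By this lower-limit criterion, power varies with the evaluable number reached (for example 68.6% at 61 and 81.9% at 72).

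Keep the half-width as a separate precision statement and do not present it as equivalent to the power.

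The cost is wording in three places and a slightly less favourable stated power. No subjects are added and no analysis changes. SAP section 4 matters most, because SAP section 3 says the SAP supersedes the protocol's statistical section. The two protocol places need an amendment, which Protocol 5.1 makes subject to ethics review.

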5 STATISTICAL METHODS

Statistical analyses will be reported using summary tables, graphs and data listings. In general, continuous variables will be summarized with mean, standard deviation (SD), median, minimum, and maximum. Categorical variables will be summarized with counts and percentage of subjects in corresponding categories.

5.1 Study Endpoints

5.1.1 Primary Endpoint

- Activity will be evaluated by complete response rate, which is defined as the proportion of subjects achieving 100% clearance of all treated AK lesions on the face or scalp at Day 57.

5.1.2 Secondary Endpoints

- Activity: Reduction in lesion counts during Days 1-57
- Safety: Evaluation of adverse events (AEs), local skin reactions (LSRs) and clinical laboratory data; the results of other safety assessments (vital signs, physical examinations, ECGs) will also be evaluated

5.1.3 Exploratory Endpoints

- Recurrence rate will be estimated with a Kaplan-Meier method for subjects who achieved 100% clearance at Day 57 (Visit 10) with any identified AK lesions on the treatment area at 3, 6, 9, and 12 months post-Day 57.
- Sustained response rate will be estimated with the same Kaplan-Meier method for subjects who achieved 100% clearance at Day 57 (Visit 10) without any identified AK lesions on the treatment area at 12 months post-Day 57.

5.2 Study Subjects

5.2.1 Definitions of Analysis Sets

- Per-Protocol Set: the group of protocol-eligible subjects who receive 5 days (Cohort 1) or 3 days (Cohort 2) of study treatment and complete at least one scheduled post-treatment AK lesion evaluation
- Evaluable Set: the group of protocol-eligible subjects who receive 5 days (Cohort 1) or 3 days (Cohort 2) of treatment and complete Day 1 and Day 57 AK lesion evaluations
- Safety Analysis/Full Analysis Set: the group of subjects who receive at least one dose of study treatment
- Recurrence Follow-up Set: the group of subjects who achieve complete clearance at Day 57

5.2.2 Subject Disposition

For screen failure subjects, a listing will be provided to present their screen failure reasons.

The number of subjects in each analysis set (Safety/Full Analysis, Per-Protocol, Evaluable, and Recurrence Follow-up) will be tabulated by cohort.

For the Safety/Full Analysis Set, subject disposition will be summarized by cohort for:

- Subjects dosed
- Subjects who completed the Day 57 visit
- Subjects who achieved 100% AK clearance at the Day 57 visit
- Subjects who discontinued before the Day 57 visit and their primary reason for discontinuation

In addition, the number of subjects dosed and the number of subjects who completed the Day 57 visit will be summarized by study site and cohort.

A listing of those subjects who discontinued before the Day 57 visit and the associated reasons will be presented.

For the Recurrence Follow-up Set, the recorded discontinuation reasons will be reviewed and subjects who discontinued early due to AK recurrence will be assigned “AK Recurrence” as the new primary reason for discontinuation.

Subject disposition will be summarized by cohort for:

- Subjects who entered the Recurrence Follow-up Period
- Subjects who completed the Recurrence Follow-up Period
- Subjects who discontinued during the Recurrence Follow-up Period and their primary reason for discontinuation

Subjects who discontinued during the Recurrence Follow-up Period will also be listed.

5.2.3 Protocol Deviations

Any protocol deviations identified during site monitoring will be captured on the eCRF. A listing with protocol deviation details will be presented.

5.2.4 Demographic and Other Baseline Characteristics

Demographic data and baseline characteristics will be analyzed for the Safety/Full Analysis Set, the Per-Protocol Set, the Evaluable Set, the Recurrence Follow-up Set, the subjects with recurrence in the Recurrence Follow-up Set and the subjects without recurrence at 12 Months Post-Day 57 Visit in the Recurrence Follow-up Set.

Demographic data, including age (in years), age category (<65, ≥65), sex, race, and ethnicity will be summarized by cohort.

Baseline characteristics, including location of treatment area (face or scalp), Fitzpatrick skin type, baseline weight, primary diagnosis of treatment area, and baseline AK lesion count will be summarized by cohort.

Demographic and baseline characteristic data mentioned above will be presented in data listings for the Safety/Full Analysis Set only.

Other baseline data, including AK history, AK treatment history, medical history for non-AK conditions, and surgical history for non-AK conditions will be listed for the Safety/Full Analysis Set.

5.2.5 Prior and Concomitant Therapy

5.2.5.1 Prior and Concomitant Medications

Non-study treatment medications will be recorded on the eCRF from 28 days before Day 1 through the final study visit. All verbatim terms collected will be coded with the World Health Organization Drug Dictionary (WHO-DD) March 1, 2017.

Prior medications will be defined as medications that stopped before the first dose of study treatment.

Concomitant medications will be defined as medications that (1) started before the first dose of study treatment and were continuing at the time of the first dose of study treatment, or (2) started on or after the date of the first dose of study treatment. Since it may not be able to determine medication dates relative to the first dose of study treatment due to partial or missing dates, if a medication cannot be determined to be 'prior' (ie, before the first dose of study treatment), it will be considered a concomitant medication.

Furthermore, to identify medications that start before the Recurrence Follow-up Period, start dates will be compared with the actual Day 57 visit date for each subject. If a medication start date cannot be confirmed to fall in the Recurrence Follow-up Period due to missing or partial dates, this medication will be considered to have started before this period.

The number and percentage of the subjects with concomitant medications starting before the Recurrence Follow-up Period will be summarized for the Safety/Full Analysis Set:

- 1) by anatomical therapeutic chemical class, standardized drug name, and cohort
- 2) by standardized drug name and cohort

The incidence of concomitant medications in the Recurrence Follow-up Period (i.e. those start after Day 57 visit) will be summarized in the same way, but separately.

In addition, a listing of all prior and concomitant medications collected throughout the entire study will be provided.

